9.1 Study endpoints

9.1.1 Primary outcome

Reduction in HbA1c or MAGE from baseline to the end of the intervention (week 24) between and within each of the two study groups (BCC and control).

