13.2 Statistical methods

Intention-to-treat (ITT) analysis will be performed as the primary analysis on all primary and secondary outcomes after the last participant has participated in the last visit. Missing values will be handled with a last observation carried forward approach for ITT analysis. Per-protocol (PP) analysis will only be performed in case of sensitivity testing.

Parametric tests (general linear models) will be used to test differences in outcomes from baseline to follow-up. Heterogeneity in responsiveness to the interventions will be tested by dividing each intervention group into smaller groups based on data distribution (medians) or clinically meaningful cut-points. If model assumptions cannot be met even after logarithmic transformation, non-parametric tests will be used. Plots of residuals versus predicted values will be used to judge normality. Metabolic patterns will be tested with multivariate statistics. Adjustment for relevant confounders will be performed. Two-sided tests will be used. *P* values of <0.05 are considered significant. The statistical programs SPSS and SAS will be used for data analysis.

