Secondary objectives were to describe changes associated with the intervention on other clinically relevant metabolic changes (body weight, body composition, blood pressure and lipid profile), changes in skills related to numeracy and carbohydrate estimation accuracy as well as on psychosocial and behavioural outcomes at the end of the intervention period and after 6 months of follow-up to assess long-term maintenance.

Hypotheses for the primary outcomes:

1. We hypothesize that BCC is superior compared with usual dietary care as stand-alone treatment (the control group) in reducing HbA1c or MAGE from baseline to end-of-treatment at week 24 (from V1 to V2).

Superiority is claimed if:

- a. the 95% confidence interval for the estimated difference in change between the groups for HbA1c or MAGE, estimated using a baseline corrected linear mixed model, excludes 0 and the P-value is <0.05: and,
- b. the estimated difference in HbA1c or MAGE between the two groups is equal to/surpass the minimal important difference in favour of the BCC group.

Hypotheses for the secondary outcomes can be found in the study protocol and clinicaltrials.gov.

Section 3: Study Methods

Trial design

Single-centre parallel-group, randomized controlled, open-label, superiority trial. Allocation ratio 1:1 to either BCC or control (usual dietary care).

Randomization

Participants were randomized using block randomization by stratifying participants based on sex, BMI and HbA1c at baseline. The randomization list was generated by an external statistician and uploaded to the electronic data management system REDCap (8.10.18, Vanderbilt University, TN, USA). Participants eligible for inclusion in the study according to the screening were randomized at the end of the screening visit (V0) by the study investigator/study personnel using the randomization module in REDCap. Baseline measurements were collected at the following baseline visit (V1) for all participants.

Sample size

See study protocol.

Framework

Superiority trial. See Objectives section.

Statistical interim analyses and stopping guidance

No interim analyses were planned and no guidelines for terminating the trial early was made.

Timing of final analyses

The results will be analysed when this statistical analysis plan has been uploaded at clinicaltrials.gov

Timing of outcome assessments

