HbA1c was measured at the screening visit (V0), at the baseline visit (V1), after 12 weeks of intervention, after 24 weeks (V2) of intervention, and after six months follow-up (V3). MAGE was measured after the baseline visit (V1), and after 24 weeks of intervention (after V2).

See section 6: Analyses for timing of secondary and descriptive/explorative outcome assessments.

Section 4: Statistical Principles

Confidence intervals and P values

Two-sided P-values and 95% confidence intervals will be presented for comparisons between groups. Two-sided 95% confidence intervals will be presented for within group comparisons and estimated levels.

Primary outcome: The direction and size of the estimated mean effect for HbA1c and MAGE (primary outcomes), in addition to the 95% confidence intervals, will be required to support the tested hypothesis for the results to be declared in accordance with the hypothesis (see section 2 under “Objectives”).

Secondary outcomes: False detection rate (FDR) correction ad modum Benjamini and Hochberg (16) will be used to control for multiplicity; < 5% will be used as the threshold for FDR.

Completers and protocol deviations

Completers: Participants who participated in an assessment of at least one of the primary outcomes at V2 and/or V3.

Lost to follow-up: Participants who did not participate in assessment of primary outcomes at V2.

Excluded for statistical data analyses: Participants in both study groups dropping out or lost to follow-up before baseline measurements have been collected.

Protocol deviators: None of the participants in the two study groups are considered protocol deviators.

Analysis populations

Efficacy estimates based on intention-to-treat (ITT) analysis set:

All participants will be analysed as randomised.

Section 5: Trial Population

Screening data

The following data obtained at the screening visit will be included for those that entered the trial:

- Age
- Self-reported sex
- Self-reported ethnicity
- Self-reported educational level
- Self-reported smoking status and number of years of smoking
- Diabetes duration

Eligibility

- Age: ≥ 18 to ≤ 75 years
- Diabetes duration: ≥ 12 months
- HbA1c: 53–97 mmol/mol
- Diet or any glucose-lowering medication
- Diagnosed with T2D and treated at Steno Diabetes Center Copenhagen

Recruitment

The flow diagram of the trial will comply with the most recent CONSORT guidelines for Reporting Outcomes in Trial Reports and includes:

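### The SAP gives two conflicting rules for combining HbA1c and MAGE into a superiority claim, and no multiplicity method covers these two primary outcomes

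*SAP*

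**What the plan says.** **Either outcome.** Protocol 9.1.1 defines the primary outcome as "Reduction in HbA1c or MAGE from baseline to the end of the intervention (week 24"); Protocol sections 7 and 8.1 use the same *or*. The SAP (Objectives, hypotheses for the primary outcomes) repeats it: BCC is to be superior "in reducing HbA1c or MAGE from baseline to end-of-treatment at week 24". Two conditions, joined by *and*, make the claim:

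- (a) "the 95% confidence interval for the estimated difference in change between the groups for HbA1c or MAGE" excludes 0, with p<0.05;
- (b) the estimated difference in HbA1c or MAGE "is equal to/surpass the minimal important difference in favour of the BCC group". SAP Section 6 sets the MIDs at 3 mmol/mol and 0.3 mmol/l.

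Neither condition says that the outcome meeting (a) must be the one meeting (b).

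**Both outcomes.** SAP Section 4 (Confidence intervals and P values) says that "The direction and size of the estimated mean effect for HbA1c and MAGE (primary outcomes"), together with the confidence intervals, must support the hypothesis. It refers back to the Objectives. The SAP's primary objective also joins the two outcomes with *and*.

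**Multiplicity.** The only method named is "False detection rate (FDR) correction ad modum Benjamini and Hochberg", for secondary outcomes. Protocol 13.2 says "Two-sided tests will be used" and that P "values of <0.05 are considered significant", with no adjustment. Protocol 13.3 powers HbA1c and MAGE each at the full two-sided 0.05. No split, order or hierarchy is given for the two primaries.

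**The concern.** The sentence that decides whether the trial succeeded can be read in two ways. If HbA1c succeeds and MAGE does not, or the reverse, the Objectives support a claim of superiority and Section 4 can be read as denying it. The choice would then be made after the results are known, in an open-label trial.

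The two readings also have different statistical needs. If either outcome suffices, there are two chances of a false claim, and a plan normally states how that is handled. If both are required, no alpha adjustment is needed, but the chance of success is much lower. The plan adopts neither reading explicitly and states no strategy for the two primary p-values.

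**Working it through.** **Inputs.** From Protocol 13.3: HbA1c difference 3.0, SD 7; MAGE difference 0.30, SD 0.7; two-sided 0.05; 80% power; 87 per group net; 113 per group enrolled; about 30% dropout. From SAP Section 6: MIDs of 3 and 0.3. The documents do not give the correlation between the two test statistics; independence and 0.5 are shown as assumptions.

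**The plan's own figure.** n = 2(1.960+0.842)²(7/3)² ≈ 85.5, so 86 per group by normal approximation. The t-test version gives 86.4, so 87 per group and 174 in total, as stated. MAGE has the same standardised effect (0.30/0.7 = 3.0/7). A 30% loss from 113 leaves about 79, so 79 and 87 are used below.

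**Unadjusted p-values.** P(at least one two-sided p<0.05 under the null) = 1 − 0.95² = 9.75% if independent; 9.1% at correlation 0.5 (bivariate normal). In the direction favouring BCC only: 1 − 0.975² = 4.94%, against 2.5% for one outcome.

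**The SAP claim, (a) and (b) on the same outcome.** A claim needs z > max(1.96, MID/SE), with SE = SD·√(2/n). Either-outcome rates below assume independence.

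| HbA1c SD / MAGE SD | n per group | MID/SE (HbA1c; MAGE) | False-claim rate per outcome | Either outcome |
|---|---|---|---|---|
| 7 / 0.7 | 87 | 2.83; 2.83 | 0.24%; 0.24% | 0.47% |
| 7 / 0.7 | 79 | 2.69; 2.69 | 0.35%; 0.35% | 0.71% |
| 7 / 1.0 | 87 | 2.83; 1.98 | 0.24%; 2.39% | 2.6% |
| 7 / 1.0 | 79 | 2.69; 1.89 | 0.35%; 2.5% | 2.8% |
| 10 / 1.0 | 79 | 1.89; 1.89 | 2.5%; 2.5% | 4.9% |

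For example, row four is 1 − (1 − 0.0035)(1 − 0.025) = 2.8%. At correlation 0.5 the last row is 4.5%. Condition (b) stops binding when 1.96·SE = MID, that is, at an HbA1c SD of about 9.6 (79 per group) or 10.1 (87 per group). Beyond that the either-outcome rate stays at 4.94%.

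**(a) and (b) on different outcomes.** At the planning SDs this changes nothing, because an estimate at the MID is already significant (2.69 > 1.96). By simulation (79 per group, independent), with both SDs scaled together, it gives 5.0% at HbA1c SD 10 and 5.7% at SD 20.

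**How often *or* and *and* disagree.** Take true differences equal to the MIDs and the planning SDs. Each outcome then reaches its MID with probability 0.50. If independent, either succeeds with probability 1 − 0.5² = 75% and both with 0.5² = 25%; the two sentences conflict in the other 50%. At correlation 0.5, P(both) = 1/4 + arcsin(0.5)/(2π) = 1/3, and they conflict in 1 − 2/3 = 1/3 of trials.

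**The case against.** The strongest reply is that condition (b) already limits the error. At the planning SDs a false claim for BCC is well under 1%, and with (a) and (b) on one outcome it cannot exceed 4.94% at any SD. This stands. A reader might infer from the 9.75% that the error rate of the superiority claim is uncontrolled. The documents do not support that: 9.75% describes two unadjusted two-sided p-values, includes results favouring control, and leaves out (b).

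The larger figures also need care. HbA1c SD 10 appears nowhere in the documents, and Protocol 13.3 says that SD 7 resembled the site's own course data. MAGE SD 1.0 does appear there, but for a cited study. With all 113 per group analysed, even SDs of 10 and 1.0 give only 2.4% (independent). What remains is that the protection is incidental: it depends on the observed standard errors, the SAP does not present it as multiplicity control, and it does not reach the reported p-values.

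It can also be said that Section 4 merely names the two outcomes and defers to the Objectives. That is a fair reading, and *or* is the more frequent wording. But Section 4 is phrased as a requirement, so the other reading remains open.

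**Conclusion.** The point holds as a defect in the success rule and a gap in the multiplicity plan, and should be fixed. The *or* and *and* wordings conflict, (a) and (b) are not tied to the same outcome, and no method covers the two primary p-values. A split result could be declared either way.

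A false claim of superiority is about 0.5–0.7% at the planning SDs (87 or 79 per group), 2.6–2.8% with MAGE SD 1.0 and HbA1c SD 7, and up to 4.9% with 79 per group if the SDs are about 10 and 1.0; the benchmark for one outcome is 2.5%. These figures assume independent outcomes and (a) and (b) on the same outcome. For the p-values alone, the chance of at least one below 0.05 is 9.75% (9.1% at correlation 0.5).

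**What to change.** State one rule in the SAP before the between-group results are analysed:

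- Keep the rule that either outcome suffices, as in the hypothesis.
- Require (a) and (b) to be met by the same outcome.
- Apply Holm to the two week-24 between-group p-values: the smaller against 0.025 and, if that is met, the larger against 0.05. Let the Holm decision replace the unadjusted p<0.05 and 95% CI test in (a); the 95% CIs can still be reported as estimates.
- Reword Section 4 to match.

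**Cost.** Wording only, with no new data. On significance alone, if MAGE shows nothing, HbA1c is tested at 0.025 and its power for 3.0 with SD 7 falls from 76% to 67% (79 per group). Power to claim superiority under the SAP rule is unchanged at the planning SD: the MID sits at z = 2.69, already above Holm's first step of z = 2.24, and power at a true difference of 3.0 is 50% with or without Holm. Holm begins to bind once the HbA1c SD exceeds 3/(2.24 × √(2/79)) ≈ 8.4.

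A fixed order, HbA1c then MAGE, is an alternative. It costs HbA1c no power but bars a claim on MAGE alone, which the stated hypothesis allows.

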Evidence suggest that a hands-on, learning-by-doing approach (problem- and experience-based patient education) can support the development of food skills in general, and improve diet quality in particular (32). Adding group-based dietary approaches to individual lifestyle counselling has also been found to improve dietary habits (33). Similarly adding diabetes self-management approaches to the diabetes education lead to lower dropout rates, increased self-efficacy and improved HbA1c in patients with T2D (34). This may be due to the fact that diabetes self-management education supports achieving personal goals for behaviour change that in turn could lead to better clinical outcomes.

The sparse scientific knowledge about the effect of BCC underlines the need for investigating and evaluating this in a practice-based group educational approach and examining the effect on improved metabolic control in patients with T2D.

In a small pre-post design study of 29 participants with T2D conducted at Steno Diabetes Center Copenhagen (SDCC) we found that patients offered a structured group education program in BCC improved their carbohydrate counting skills (p<0.001) and reported increased knowledge concerning types and amounts of carbohydrates and how to prevent hyper- or hypoglycaemia. However, no significant changes in HbA1c (p=0.08) or body weight (p=0.616) where found after six months (unpublished data). Despite the limited clinical effects in this small study the initial results are interesting and call for additional research in a stronger randomized set-up and with power to investigate whether a group-based dietitian-delivered program in BCC has an independent effect on glycaemic control and body weight management in patients with T2D in up to 12 months to assess if dietary adherence to the BCC program is still high after one year.

7 Main hypothesis

Training and education in the BCC concept will improve glycaemic control either by reducing HbA1c or the average plasma glucose variability more than offering a standard nutrition education (control) as a stand-alone dietary treatment. The underlying mechanisms are that nutrition education in BCC will improve the patients' knowledge and awareness of the ingested amount of carbohydrates, the accuracy of carbohydrate estimation together with focus on higher consistency (reduced variability) in the carbohydrate intake, all of which will reduce glucose variability and HbA1c.

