13.3 Determination of sample size

Allowing for drop-outs (~30%) and subgroup analyses we plan to include a total of 226 patients in our study. This is based on sample size calculations which suggested that including 87 participants in each of the study groups would give us 80% power to detect a clinically meaningful difference in change in HbA1c of 3.0 mmol/mol between the BCC group versus the control group with a 5% significance level using a two-sided test and an estimated standard deviation (SD) of 7 mmol/mol. This SD and dropout rate have previously been used for sample size calculations and were similar to what we found when evaluating our BCC courses on dropout rate, mean changes and SD of HbA1c after 6 months in completers with T2D. MAGE has only been used as an outcome measure of glucose variability in a few randomized controlled dietary intervention studies of patients with diabetes (40, 41) showing differences in changes in MAGE up to 4.8 mmol/l (SD: 1.0) after a 12-week carbohydrate counting intervention (40). By including 113 participants in each study group we will have a power of 80% (alpha level of 0.05) in a two-sided test to detect a clinically meaningful difference in the change in MAGE during the intervention period (24 weeks) of \geq 0.30 mmol/l (SD 0.7 mmol/l) between the study groups as presented in **Table 5**.

Difference in HbA1c, mmol/mol (SD 7.0)	Difference in MAGE, mmol/l (SD 0.7)	Net no of participants in the study (BCC vs control)	No of participants given a dropout rate of 30%
2.0	0.20	388	504
3.0	0.30	174	226
3.5	0.35	128	166
4.0	0.40	100	130

Table 5: Sample size calculations

14 Data management

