Estimation of minimal important difference for primary outcome: Reductions in HbA1c of 3 mmol/mol and 0.3 mmol/l of MAGE were defined as minimal important differences in this trial. This was primarily based on findings from clinical trials of different dietary approaches for reducing HbA1c in T2D (18, 19). Since no studies had examined the effect of dietary interventions using MAGE as an outcome in our target population with T2D at the time. Thus, based on previous findings (18, 19) we expected to find HbA1c reductions around 3 mmol/mol compared to standard care. This was considered clinically relevant as part of a multidisciplinary approach for the management of hyperglycaemia in T2D.

Secondary/descriptive/exploratory outcomes

The treatment effect will be given as the baseline corrected difference between the groups at V2 and V3. No minimal clinically relevant differences were defined for these outcomes.

- HbA1c (mmol/mol) (only for V3)
- Total body weight (kg), women
- Total body weight (kg), men
- BMI (kg/m²)
- Blood pressure
 - Systolic blood pressure (mmHg)
 - Diastolic blood pressure (mmHg)
- Fasting concentration of plasma lipids
 - Total cholesterol (mmol/l)
 - LDL cholesterol (mmol/l)
 - HDL cholesterol (mmol/l)
- Anthropometry
 - Waist circumference, cm (women)
 - Waist circumference, cm (men)
 - Waist/Hip ratio, unitless (women)
 - Waist/Hip ratio, unitless (men)
- Blinded CGM data (not measured at V3)
 - Mean plasma glucose, mmol/l
 - Time in range (TIR): % of readings and time 3.9-10.0 mmol/l
 - Time above range (TAR): % and readings and time 10.1-13.9 mmol/l
 - Time below range (TBR): % readings and time 3.0-3.8 mmol/l
 - Glycaemic variability, coefficient of variation (CV), %
 - Glycaemic variability, standard deviation (SD), mmol/l
- Numeracy skills test

- Total score
- Correct answers, n and %
- Carbohydrate estimation accuracy test based on 11 high-carb foods (only for foods reported eaten)
 - Estimation errors in %
- Self-reported diabetes diet-related quality of life (DDRQOL), total score within each subscale
 - General perception of diet
 - Satisfaction with diet
 - Restriction of social functions
 - Burden of dietary therapy
 - Perceived benefits of dietary therapy
 - Mental health
 - Vitality
- Self-reported Perceived Health Competence Scale (PCS), total score
- Self-reported Healthcare Climate Questionnaire (HCCQ) (not measured at V3), total score
- Dietary intake (not measured at V3)
 - Total energy intake (kJ/day)

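### The SAP's superiority rule succeeds only 50% of the time per outcome at the planned effect, while the only power it adopts is 80% for p<0.05 alone; its sections also differ on 'or' versus 'and'

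*SAP*

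**What the plan says.** SAP Section 2 states the hypothesis that BCC is superior to usual dietary care "in reducing HbA1c or MAGE from baseline to end-of-treatment at week 24". A claim needs two conditions. Condition (a) is a 95% confidence interval that excludes 0, with p<0.05. Condition (b) is that "the estimated difference in HbA1c or MAGE between the two groups is equal to/surpass the minimal important difference in favour of the BCC group". SAP Section 6 fixes the thresholds: "Reductions in HbA1c of 3 mmol/mol and 0.3 mmol/l of MAGE were defined as minimal important differences in this trial". It adds that an HbA1c effect of about that size was expected.

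For sample size, SAP Section 3 says only "See study protocol". Protocol section 13.3 says that 87 participants per group "would give us 80% power to detect a clinically meaningful difference in change in HbA1c of 3.0 mmol/mol", using a two-sided 5% test and an SD of 7 mmol/mol. For MAGE it plans on 0.30 mmol/l with an SD of 0.7 mmol/l. Neither calculation puts a condition on the size of the estimate.

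On how the two outcomes combine, SAP Section 2 uses 'or' in the hypothesis and in both conditions. Protocol sections 7, 8.1 and 9.1.1 do the same; section 7 says that BCC "will improve glycaemic control either by reducing HbA1c or the average plasma glucose variability". SAP Section 4, however, refers to the direction and magnitude of the "mean effect for HbA1c and MAGE (primary outcomes), in addition to the 95% confidence intervals, will be required to support the tested hypothesis", and points back to Section 2.

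**The concern.** The threshold in (b) equals the effect the trial was sized to detect. An unbiased estimate of a true 3.0 mmol/mol falls below 3.0 in half of all trials, so the chance of a superiority claim at the planned effect cannot be 80%. A reader who follows the SAP's reference to the protocol will take 80% as the chance of success and will over-read a failed claim as evidence against BCC.

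The second issue is the verdict when only one outcome meets the rule. Under Section 2 the hypothesis is then supported. Under a literal reading of the Section 4 sentence it is not. As worded, (a) and (b) also need not be met by the same outcome. In an open-label trial these choices should be settled before the results are known.

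**Working it through.** **Inputs.** From protocol section 13.3: SD 7 mmol/mol (HbA1c) and 0.7 mmol/l (MAGE), planned differences 3.0 and 0.30, two-sided 5%, 87 per arm net of drop-out, 113 per arm randomised. From SAP Section 6: thresholds 3 and 0.3. I also use 79 per arm, which is 113 × 0.70 after a 30% loss. The correlation between the two estimates is not in the documents, so I show 0 to 0.9.

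**The plan's own figure.** A two-sample t-test with difference 3.0 and SD 7 needs 87 per arm (174 in total) for 80% power, as stated; power at 87 is 80.3%. MAGE has the same standardised effect (0.30/0.7 = 3.0/7 = 0.43), so the result is identical. The 80% belongs to the net 87 per arm in Table 5; at 113 per arm it would be 89%.

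**Per outcome.** SE = 7 × √(2/n). MAGE values are one tenth of those for HbA1c.

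| n per arm | SE (HbA1c) | Smallest significant estimate | Power, (a) alone | (a) and (b) | Significant but below threshold |
|---|---|---|---|---|---|
| 79 | 1.114 | 2.20 | 76.3% | 50% | 26% |
| 87 | 1.061 | 2.09 | 80.3% | 50% | 30% |
| 113 | 0.931 | 1.84 | 89.4% | 50% | 39% |

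The smallest significant estimate lies below 3.0 at each n, so (b) is the binding condition and success at a true 3.0 is P(estimate ≥ 3.0) = 0.50. This holds whenever the SE is below threshold/1.96, that is 3/1.96 = 1.53 mmol/mol or 0.153 mmol/l. More participants do not raise it. Nor does the SAP's baseline-corrected model: a smaller SE leaves the estimate centred on the same value.

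**Both outcomes, true effects equal to the thresholds, 87 per arm.** P(both) = 1/4 + arcsin(ρ)/(2π); P(at least one) = 1 − P(both); P(exactly one) = 1 − 2 × P(both).

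| ρ (assumed) | At least one, rule | At least one, p<0.05 only | Both, rule | Exactly one, rule |
|---|---|---|---|---|
| 0 | 75.0% | 96.1% | 25.0% | 50.0% |
| 0.5 | 66.7% | 91.4% | 33.3% | 33.3% |
| 0.9 | 57.2% | 85.2% | 42.8% | 14.4% |

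A patient-level simulation (40,000 trials) agrees to within half a percentage point. If only one outcome has its planned effect and the other has none, the 'or' rule gives 50%, against 80–81% for p<0.05 alone.

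**True difference needed for 80% under the rule.** 3 + 0.8416 × SE = 3 + 0.8416 × 1.061 = 3.89 mmol/mol at 87 per arm (3.94 at 79, 3.78 at 113), or 0.39 mmol/l for MAGE. Under a baseline-corrected model the effective SD is 7 × √((1+r)/2). For assumed baseline to week-24 correlations r of 0.3, 0.5 and 0.8 this is 5.64, 6.06 and 6.64, giving 3.72, 3.77 and 3.85 mmol/mol.

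**MAGE SD.** The protocol also cites a study "showing differences in changes in MAGE up to 4.8 mmol/l (SD: 1.0"). It is unclear what that SD measures. If 1.0 applied, then at 79 per arm significance would start at 0.314 mmol/l, (b) would no longer imply (a), and MAGE success at a true 0.30 would be 46%. At 87 and 113 per arm it stays at 50%.

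**The case against.** The strongest reply is that nothing false has been stated. The protocol's 80% is correct for the test it describes, and neither document says that 80% is the chance of meeting the Section 2 rule. The 50% is inherent in any rule whose threshold equals the planned effect, the sample size can no longer respond, and the SAP reports estimates with confidence intervals, so a significant 2.5 mmol/mol would be visible to any reader. This is fair: the gap is an undisclosed property of the rule, and the validity of the estimates is not in question. But the SAP introduces its own decision rule and gives no power except by reference to a figure for a different rule. That affects how a failed claim is read.

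On 'or' versus 'and', the SAP elsewhere uses both names as a plain list of the primary outcomes, and the Section 4 sentence refers back to Section 2. I agree that 'or' is the likelier reading; this is an ambiguity, not a firm contradiction.

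Three smaller points also stand. The same-outcome wording changes no verdict at the planned inputs, because there (b) on an outcome implies (a) on that outcome. The SD of 1.0 comes from a study whose title names adults with type 1 diabetes, so that scenario is only a caution. And the rule has a benefit: if BCC has no effect, a favourable claim occurs in about 0.24% of trials per outcome at 87 per arm (P(Z ≥ 3/1.061)).

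**Conclusion.** The concern holds and should be fixed before analysis. At the planned effects the SAP's rule succeeds with probability 50% per outcome, against 80% for the test alone. About 30% of trials would give a significant HbA1c result, with an estimate from about 2.1 to just under 3.0 mmol/mol, that fails the rule. On the 'or' reading with both effects as planned, success is 57–75% against 85–96%; no non-negative correlation brings the rule to 80%. If exactly one outcome meets the rule (14–50% of trials in that setting), Sections 2 and 4 can give opposite verdicts.

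The 50% needs only an estimate distributed symmetrically around a true effect equal to the threshold, and an SE below 1.53 mmol/mol or 0.153 mmol/l. The two-outcome figures rest on the assumed correlation and on both true effects equalling their thresholds. The issue is undisclosed low power; the rule does not inflate false-positive claims.

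**What to change.** Keep condition (b), and change the wording in two places.

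1. In the SAP sample-size section add: *The protocol's 80% power refers to the two-sided 5% test alone. Under the Section 2 rule the probability of success is 50% per outcome if the true difference equals the minimal important difference; 80% per outcome needs a true difference of about 3.9 mmol/mol or 0.39 mmol/l (change-score SE, SD 7 or 0.7, 87 per arm).* For HbA1c under the SAP's own model, about 3.7–3.9 could be given with its assumed correlations. If a figure for at least one outcome is added, state the correlation: 57% at 0.9, 67% at 0.5, 75% at 0. The low false-claim rate of the rule can be stated alongside.

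2. In Section 2 write: *Superiority is claimed for an outcome only if (a) and (b) both hold for that same outcome; the hypothesis is supported if this is so for at least one of HbA1c and MAGE.* Align the Section 4 sentence with it. If both outcomes are meant to be required, say so in both sections and state a success probability of about 25–43%.

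The cost is SAP wording only. The success threshold, model and reported estimates do not change, and nothing is loosened after open-label data collection. The stated chance of success becomes less favourable, and the authors must commit to 'or' or 'and' before seeing results.
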